8.2.3 Health-related quality of life physical component

Secondary efficacy endpoint:

The treatment effect of Flebogamma[®] 5% DIF compared to placebo on HRQoL will be calculated as the least squares means difference between treatment groups in the change in SF-36 PCS score from baseline (at EV/IV1) to the end of the treatment period (at the EoTV – Week 52).

Exploratory endpoint:

The sustained effect of Flebogamma® 5% DIF compared to placebo on HRQoL will be calculated as the least squares means difference between treatment groups in the change in SF-36 PCS score from baseline (at EV/IV1) to 12 and 24 weeks after the last investigational product infusion, that is, at FU3 and at the FV.

8.2.4 Endurance

Secondary efficacy endpoint:

The treatment effect of Flebogamma[®] 5% DIF compared to placebo on endurance will be calculated as the least squares means difference between treatment groups in the change in 6MWD from baseline (at EV/IV1) to the end of the treatment period (at the EoTV – Week 52).

Exploratory endpoint:

The sustained effect of Flebogamma® 5% DIF compared to placebo on endurance will be calculated as the least squares means difference between treatment groups in the change in 6MWD from baseline (at EV/IV1) to 12 and 24 weeks after the last investigational product infusion, that is, at FU3 and at the FV.

8.2.5 Muscle strength

Exploratory endpoints:

The treatment effect of Flebogamma® 5% DIF compared to placebo on muscle strength will be calculated as the least squares means difference between treatment groups in the change in MRC score and in QMT score from baseline (at EV/IV1) to the end of the treatment period (at the EoTV – Week 52).

The sustained effect of Flebogamma[®] 5% DIF compared to placebo on muscle strength will be calculated as the least squares means difference between treatment groups in the change in MRC score and in QMT score from baseline (at EV/IV1) to 24 weeks after the last investigational product infusion, that is, at the FV.

Sites affected by the COVID-19 pandemic can refer to ANNEX 18 for extraordinary contingency measures to be implemented.

8.2.6 Walking activity in daily life

Exploratory endpoints:

The treatment effect of Flebogamma[®] 5% DIF compared to placebo on walking activity in daily life will be calculated as the least squares means difference between treatment groups in the change in number of steps performed during 7 consecutive days prior to the scheduled visit, from baseline (at EV/IV1) to the end of the treatment period (at the EoTV – Week 52).

The sustained effect of Flebogamma® 5% DIF compared to placebo on walking activity in daily life will be calculated as the least squares means difference between treatment groups in the change in number of steps performed during 7 consecutive days prior to the scheduled

visit, from baseline (at EV/IV1) to 24 weeks after the last investigational product infusion, that is, at the FV.

8.2.7 Perceived exertion/fatigue

Exploratory endpoint:

The treatment effect of Flebogamma[®] 5% DIF compared to placebo on self-perceived exertion/fatigue using the Borg scale will be calculated as the least squares means difference between treatment groups in the change in Borg scale from baseline (at EV/IV1) to the end of the treatment period (at the EoTV – Week 52).

The sustained effect of Flebogamma[®] 5% DIF compared to placebo on self-perceived exertion/fatigue using the Borg scale will be calculated as the least squares means difference between treatment groups in the change in Borg scale from baseline (at EV/IV1) to 12 weeks and 24 weeks after the last investigational product infusion, that is, at FU3 and at the FV.

8.2.8 Fatigue

Exploratory endpoints:

The treatment effect of Flebogamma[®] 5% DIF compared to placebo on fatigue will be calculated as the least squares means difference between treatment groups in the change in FSS from baseline (at EV/IV1) to the end of the treatment period (at the EoTV – Week 52).

The sustained effect of Flebogamma[®] 5% DIF compared to placebo on fatigue will be calculated as the least squares means difference between treatment groups in the change in FSS from baseline (at IV1) to 24 weeks after the last investigational product infusion, that is, at the FV.

8.2.9 Health-related quality of life mental component

Exploratory endpoints:

The treatment effect of Flebogamma[®] 5% DIF compared to placebo on HRQoL will be calculated as the least squares means difference between treatment groups in the change in SF-36 MCS score from baseline (at EV/IV1) to the end of the treatment period (at the EoTV – Week 52).

The sustained effect of Flebogamma[®] 5% DIF compared to placebo on HRQoL will be calculated as the least squares means difference between treatment groups in the change in SF-36 MCS score from baseline (at EV/IV1) to 12 and 24 weeks after the last investigational product infusion, that is, at FU3 and at the FV.

8.2.10 Inflammatory cytokines

Exploratory endpoints:

The treatment effect of Flebogamma® 5% DIF compared to placebo on inflammatory cytokines will be calculated as the least squares means difference between treatment groups in the change in blood inflammatory cytokine levels from baseline (at EV/IV1) to the end of the treatment period (at the EoTV – Week 52).

The sustained effect of Flebogamma[®] 5% DIF compared to placebo on inflammatory cytokines will be calculated as the least squares means difference between treatment groups in the change in blood inflammatory cytokine levels from baseline (at EV/IV1) to 24 weeks after the last investigational product infusion, that is, at the FV.

9 ASSESSMENT OF SAFETY

9.1 Specification of safety parameters

Aspects of clinical safety will be evaluated in this clinical trial.

Safety endpoints will include:

- AEs and suspected ADRs.
- Vital signs during infusions.
- Physical assessments.
- Blood biochemistry and cell counts.

9.2 Methods and timing for assessing, recording, and analyzing safety parameters

Safety will be assessed throughout the clinical trial for all individuals who have received at least 1 infusion of the investigational product (test or placebo).

9.2.1 Adverse events

AEs (includes suspected ADRs) occurring at any time between signature of the subject's ICF and the last day of the subject's participation in the clinical trial will be reported and recorded on the appropriate subject's eCRF.

It is Investigator's responsibility to ensure that all AEs are appropriately recorded.

AEs will be elicited by spontaneous reporting by the study individual or by a non-leading inquiry or direct observation by the study staff.

9.2.2 Vital signs during infusions

During all treatment infusions, vital signs (T, RR, HR, SBP and DBP) will be monitored by the Investigator or study staff. Monitoring will be routinely performed within 20 minutes before the beginning of infusion as well as every 30 ± 10 minutes during the first hour of infusion. Thereafter, vital signs will be monitored and recorded at 30 ± 10 minutes post-completion of infusion. Recorded values must be reviewed (with signature and date) by a medical doctor.

Clinically relevant changes in vital signs during infusions of Flebogamma® 5% DIF or Normal Saline Solution will be reported as AEs. Clinical relevance will be based on the Investigator's judgment.

9.2.3 Physical assessment

Physical examinations will be registered as normal or abnormal, according to the medical doctor's judgment or study staff's judgment. Abnormal findings judged as clinically relevant by the Investigator will be considered AEs.

9.2.4 Blood biochemistry and cell counts

All clinical laboratory data for renal (creatinine, BUN and GFR), hepatic (ALT, AST, ALP and TBL) and haematological parameters (CBC including differential leukocyte count) will be listed for each clinical trial subjects.

The Investigator will be required to classify laboratory results out of the normal range reported by the laboratory as clinically relevant or not according to his/her judgment.

Laboratory results out of the normal range judged by the Investigator as clinically relevant will be considered AEs.

9.3 Procedures for eliciting reports of and for recording and reporting adverse event and intercurrent illnesses

9.3.1 Adverse event

An AE is defined as any untoward medical occurrence in a patient or clinical investigation subject administered a medicinal product or study treatment and which does not necessarily have a causal relationship with this administration. An AE can therefore be any unfavorable and unintended sign (including any abnormal laboratory finding, for example), symptom, or disease temporally associated with the use of a medicinal product, whether or not considered related to the medicinal product.

Any AE that occurs at any time between signature of the ICF and last day of the subject's participation in the clinical trial must be reported and recorded on the AE eCRF.

9.3.2 Suspected adverse drug reaction/adverse reaction

All noxious and unintended responses to a medicinal product or device related to any dose should be considered suspected ADRs. The phrase "responses to a medicinal product or device" means that a causal relationship between a medicinal product or device and an AE is at least a reasonable possibility, that is, the relationship cannot be ruled out. In the framework of this study, a suspected ADR with a causal relationship of "definite" will be labeled as an AR; thus, ARs are a subset of suspected ADR.

9.3.3 Causality of adverse event

The investigator is required to provide a causality assessment for each AE reported to the sponsor. The sponsor will consider the investigator's causality assessment and also provide its own assessment. Assessment of the causal relationship to the study drug will be made according to the following classifications based on Karch FE, et al. [70]:

1. Definite: An event that follows a reasonable temporal sequence from administration of the drug or in which the drug level has been established in body fluids or tissues; that follows a known response pattern to the suspected drug; and that is confirmed by

improvement on stopping the drug (dechallenge), and reappearance of the event on repeated exposure (rechallenge).

- 2. Probable: An event that follows a reasonable temporal sequence from administration of the drug; that follows a known response pattern to the suspected drug; that is confirmed by dechallenge; and that could not be reasonably explained by the known characteristics of the patient's clinical state.
- Possible: An event that follows a reasonable temporal sequence from administration of the drug; that follows a known response pattern to the suspected drug; but that could have been produced by the patient's clinical state or other modes of therapy administered to the patient.
- 4. Doubtful/Unlikely: An event that follows a reasonable temporal sequence from administration of the drug; that does not follow a known response pattern to the suspected drug; but that could not be reasonably explained by the known characteristics of the patient's clinical state.
- 5. Unrelated: Any event that does not meet the criteria above.

The operational tool to decide the AE causal relationship is based on algorithms by Karch-Lasagna and Naranjo (ANNEX 15) [71,72].

When an AE is classified, assessing causal relationship by the Investigator, as "definite", "probable," "possible" or "doubtful/unlikely," the event will be defined as a suspected ADR. A suspected ADR with a causal relationship of "definite" will be defined as an AR. When the causal relationship is labeled "unrelated," then it will be considered that the AE is not imputable to the study treatment, and it is not a suspected ADR.

In addition, when a causal relationship between the study treatment and the AE cannot be ruled out by the Investigator and/or sponsor, it means that the AE cannot be labeled "unrelated".

For any subject, all AEs that occur at any time, between the beginning of the first infusion of Flebogamma[®] 5% DIF or Normal Saline Solution and the final visit of the clinical trial, will be considered as TEAEs.

AEs occurring during the 2-day infusion period (*i.e.*, from the initiation of the investigational product infusion on the first day to the completion of the total dose of investigational product on the last day) and within 72 hours following the completion of the infusion of the total dose of investigational product on the last day, regardless of other factors that may impact a possible causal association with product administration, will be defined as infusional AEs (*i.e.*, an AE temporally associated with an infusion of the investigational product) and labeled TEAEs [73].

For AEs that occur during infusions, the infusion rate in effect at the time of onset of the AE, the time of onset of the AE and the time of AE change materially in intensity and/or resolve will be captured.

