Body weight	Normal Saline Solution (40 mL/kg body weight)	Maximum daily dose (mL) of Normal Saline Solution (20 mL/kg body weight/day)
40 kg	1600 mL	800 mL
50 kg	2000 mL	1000 mL
60 kg	2400 mL	1200 mL
70 kg	2800 mL	1400 mL
80 kg	3200 mL	1600 mL
90 kg	3600 mL	1800 mL
100 kg	4000 mL	2000 mL
110 kg	4400 mL	2200 mL

During all treatment infusions, subject's vital signs, that is body temperature (T), respiratory rate (RR), heart rate (HR), systolic blood pressure (SBP) and diastolic blood pressure (DBP), will be monitored and recorded as follows: (1) within 20 minutes before the beginning of each infusion; (2) every 30 ± 10 minutes during the first hour of each infusion; and (3) at 30 \pm 10 minutes post-completion of each infusion.

Investigational products (test and placebo) will be administered intravenously at an initial rate of 0.01 mL/kg/min for the first thirty minutes. If tolerated, advance to 0.02 mL/kg/min for the second 30 minutes. Again, if tolerated, advance to 0.04 mL/kg/min for the third 30 minutes. If the patient tolerates the infusion well, additional increments of 0.02 mL/kg/min may be made at 30-minute intervals up to a maximum of 0.08 mL/kg/min.

Individuals with predisposition to acute renal failure (such as age greater than 65 years, preexisting renal insufficiency, diabetes mellitus, hypovolaemia, overweight, concomitant nephrotoxic medicinal products), their renal function will be assessed by means of the glomerular filtration rate (GFR) at scheduled visits (see Section 4.5.2.7). Subjects with predisposition to acute renal failure but normal GFR will be infused as indicated in the previous paragraph. Subjects with predisposition to acute renal failure and abnormal GFR will be infused at the minimum practicable rate. Do not exceed the recommended dose and administer IGIV3I Grifols 5% at the minimum dose and infusion rate practicable and at less than 0.06 mL/kg/minute (3 mg/kg/minute).

The rate of infusion should be controlled by means of an infusion pump.

If an infusional AE (see Section 4.5.2.24) occurs during the first treatment course, the study staff will initiate 1 of the following actions which will be graded from 1 to 5 depending on the nature and/or severity of the event:

- 1. Does not modify the rate of the infusion upon evaluation; or
- 2. Staff reduces the current infusion rate to one-half the rate of the infusion at which the AE was observed; or

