10.1.3 Statistical analysis of safety

The safety analyses will be addressed by listing and tabulation of AEs (includes suspected ADRs), vital signs, physical assessments and clinical laboratory tests. Data will be described using descriptive analyses.

Adverse events:

Safety analysis will be primarily focused on a descriptive analysis of suspected ADRs. Safety assessment will be based on the prevalence of suspected ADRs that occurred during the clinical trial.

Adverse events will be coded and classified using MedDRA® terms (system organ class and preferred terms).

Adverse events will be classified as treatment emergent AEs (TEAEs) or non-treatment emergent AEs (non-TEAEs) depending on the comparison of AE onset date/time with the start date/time of study treatment with the investigational product. A TEAE will be defined as an AE which occurs between the beginning of the first infusion of Flebogamma® 5% DIF or Normal Saline Solution and the final visit of the clinical trial. A non-TEAE will be defined as an AE which occurs prior to the start of study treatment. Non-TEAEs and TEAEs will be summarized separately. TEAEs that occurred during the Treatment period (from the first investigational product infusion at IV1, Week 0, to the

EoTV, Week 52) and Follow-up period (from EoTV, Week 52, to the FV, Week 76) will be collectively and separately summarized.

All AEs will be summarized by presenting subject incidences and percentages, and they will also be listed by body systems with subject identification codes.

In addition, TEAEs, including suspected ADRs, will be summarized by each treatment arm, system organ class, preferred term, causal-relationship, intensity (severity) and seriousness (serious versus non-serious) using descriptive statistics. At each level of summarization, a subject will only be counted once per system organ class or preferred term using the most severe or causal relationship AE.

AEs, including suspected ADRs, of thromboembolic and hemolytic origin will also be summarized separately.

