11.1 Adverse Events

Analysis of AEs will be primarily focused on a descriptive analysis of AEs, suspected adverse drug reaction (ADRs) and adverse reaction (AR). Safety assessment will be based on the prevalence of suspected ADRs and AR occurred during the clinical trial.

- Suspected ADRs are defined as AEs with a causal relationship to study treatment of "Definitely Related", "Probably Related", "Possibly Related" or "Doubtful/Unlikely Related".
- ARs are defined as AEs with a causal relationship to study treatment of "Definitely Related".

AEs will be classified according to their onset date/time into the following categories:

Treatment emergent AEs (TEAEs): AEs with an onset date/time between first study treatment date/time and final study visit date or a pre-existing AE that worsens in severity within the same time window.

TEAEs will be further classified as follows:

- o On-treatment TEAEs: TEAEs with an onset date/time between first study treatment date/time and last study treatment date +4 weeks.
- o Infusional TEAEs: TEAEs with an onset date/time between the start date/time of study treatment infusion and 72 hours post-completion of the infusion of total dose of study treatment during any of the 2-day infusion periods.
- Post-treatment TEAEs: TEAEs with an onset date/time after the last study treatment date/time +4 weeks.
- non-TEAEs: all other AEs i.e. AE which occur prior to the start of study treatment.

For the purposes of classifying AEs into the above categories, partial AE start and end dates will be imputed to allow comparison with the study treatment date start and end dates. Section 13.1.1 below presents the imputation rules. Note, the imputed dates will be used for classification purposes only and the original partial AE dates will be presented in data listings.

AEs will be coded using MedDRA dictionary version 17.1 and summarized (stage 1 and stage 2 combined) by treatment group, system organ class (SOC) and preferred term (PT) as follows:

- TEAEs:
 - On-treatment TEAEs
 - overall
 - by maximum severity
 - by maximum causal-relationship
 - **SAEs**
 - suspected ADRs
 - ARs
 - **AESIs**
 - suspected ADRs of Special Interest (SI),
 - ARs of SI

- o Post-treatment TEAEs
 - overall
 - SAEs
- Infusional TEAEs
 - overall
 - SAEs
 - suspected ADRs
- Non-TEAEs

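### Protocol 9.3.3 sends a well-timed, known-pattern event with no dechallenge and no other explanation to Unrelated, forbids that label, and offers no other class

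*Protocol*

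**What the plan says.** Protocol 9.3.3 defines the classes as follows.

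- **Definite**: reasonable timing or an established drug level, a known response pattern, improvement on stopping, and recurrence on re-exposure.
- **Probable**: reasonable timing, and an event "that follows a known response pattern to the suspected drug; that is confirmed by dechallenge; and that could not be reasonably explained" by the patient's clinical state.
- **Possible**: reasonable timing and a known pattern, where clinical state or other therapy could have produced the event.
- **Doubtful/Unlikely**: reasonable timing, no known pattern, and not reasonably explained by clinical state.
- The fifth class is the remainder: "Unrelated: Any event that does not meet the criteria above".

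The first four classes are suspected ADRs; Unrelated is not. The last paragraph of 9.3.3 adds that, where the investigator and/or sponsor cannot rule out a causal relationship, "it means that the AE cannot be labeled" unrelated. Section 9.3.2 likewise treats a relationship that cannot be ruled out as a suspected ADR. Section 9.3.3 also refers to an operational tool in ANNEX 15, whose content is not in the supplied text.

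On analysis, Protocol 10.1.3 states: "Safety analysis will be primarily focused on a descriptive analysis of suspected ADRs". SAP 11.1 fixes the set by label: "Suspected ADRs are defined as AEs with a causal relationship to study treatment of" one of the four related classes. Protocol 9.3.8.2 makes the SUSAR unblinding step depend on the investigator's causality being anything except Unrelated.

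**The concern.** The class definitions should rank events by strength of evidence. Here, one profile with fairly strong evidence (right timing, recognised pattern, nothing else to explain it) drops to the bottom class only because the drug was not stopped or could not be.

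That profile is plausible in this trial. Protocol 2.3 lists chills, headache and fever among IVIG reactions. The first action open to staff for an infusional event in 4.4.4.3 is "Does not modify the rate of the infusion upon evaluation", which gives no dechallenge. Dosing takes two days every four weeks, and the infusional window runs 72 hours past completion, so an event may begin when no infusion is left to stop.

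At stake is how consistently one label is assigned. It decides entry to the suspected-ADR tables, which are the stated focus of the safety analysis, and it also feeds SUSAR handling.

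**Working it through.** There is no sample-size or error-rate figure to reproduce. The check is a truth table on the five definitions.

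**Inputs.** Six yes/no features from 9.3.3: reasonable timing, established drug level, known pattern, dechallenge, rechallenge, and another cause that could explain the event. (Clinical state and other therapy are merged into this last feature.) That gives 2^6 = 64 combinations, 32 of them with reasonable timing.

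**Step 1: events with reasonable timing and a known pattern.**

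| Dechallenge / rechallenge | Other cause could explain | Class on a literal reading |
|---|---|---|
| none | no | **Unrelated** |
| none | yes | Possible |
| dechallenge only | no | Probable |
| dechallenge only | yes | Possible |
| both | no | Definite and Probable |
| both | yes | Definite and Possible |

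One of these six profiles falls through. In the full enumeration it covers 2 (drug level) x 2 (rechallenge) = 4 combinations, so it falls through even with a positive rechallenge.

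**Step 2: all events with reasonable timing.** Of 32 combinations, 12 end as Unrelated: these 4, plus 2 x 2 x 2 = 8 with no known pattern and another cause, where Unrelated is unsurprising. The classes also overlap: 2 combinations meet Definite and Probable, and 2 meet Definite and Possible.

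**Step 3: neighbouring profiles.** Start from the profile that falls through and change one feature.

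- Add another possible cause: the class becomes Possible.
- Remove the known pattern: the class becomes Doubtful/Unlikely.

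Both changes weaken the case for the drug, yet both turn the event into a suspected ADR.

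**Step 4: the closing paragraph of 9.3.3.** If causality cannot be ruled out for this profile, Unrelated is barred. The definitions of the other four classes still do not fit:

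- Definite and Probable lack dechallenge.
- Possible lacks another cause.
- Doubtful/Unlikely requires that the pattern not be known.

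The profile then has no defined class.

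**Step 5: what the label does.** Under SAP 11.1 an event recorded as Unrelated is outside the suspected-ADR tables. If causality is left blank because nothing fits, Protocol 10.1.3 lists the event individually, but SAP 11.1 has no rule counting it as a suspected ADR. If any of the four related labels is chosen, the event is counted.

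**The case against.** The strongest reply is that the plan already prevents the loss. Sections 9.3.2 and 9.3.3 both turn on whether causality can be ruled out, and for an event with right timing, a known pattern and no other explanation it hardly can. If that rule is followed, the only doubt is which related class to use; all four count as suspected ADRs and nothing leaves the tables. ANNEX 15 may also settle the case. This stands, and it limits the finding to a conflict between rules.

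Three stronger readings are tempting, and the documents do not support them.

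- *A reader might infer that headache after an infusion, or a stroke, is bound to score Unrelated.* It is not. Possible needs only that clinical state or other therapy could have produced the event, a low bar in premedicated subjects aged up to 75. The documents do not say whether recovery after an infusion has ended counts as dechallenge; if it does, some of these events are Probable.
- *A reader might infer that the events disappear from safety reporting.* They remain in the on-treatment and infusional TEAE tables when they fall in those windows, in the SAE and special-interest tables where applicable, and in the listings. Protocol 10.1.3 separately summarises infusional events that are more frequent on active than on placebo. All SAEs are reported whatever their attribution, so the SUSAR step is at risk only if the closing rule of 9.3.3 is breached.
- *A reader might infer that the loss falls mainly on the active arms and narrows the contrast with placebo.* Placebo events that resemble IVIG reactions would be graded by the same definitions, and nothing in the documents sizes the difference.

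The reply does not remove the contradiction itself. Two rules in one section give different answers for the same event, and neither names a usable class.

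**Conclusion.** The contradiction in 9.3.3 is real and amounts to more than a missing detail, because the disputed label alone decides entry to the suspected-ADR tables and feeds the SUSAR step. Losing such events from those tables is a risk if an assessor applies the remainder class literally; it is not what the plan intends.

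The size is unknown. One of six profiles is a count of logical combinations, not of events. The share of reactions with this profile is not in the documents, and any assumed share would simply reappear as the assumed loss. The conclusion rests on reading the class definitions literally and on ANNEX 15 not already resolving the case, which cannot be checked here.

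**What to change.** **Protocol 9.3.3.**

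- Define Possible as reasonable timing plus a known pattern without meeting Definite or Probable, whether or not another cause could explain the event.
- Replace the remainder class with a positive definition of Unrelated: no reasonable temporal sequence, or no known pattern and reasonably explained by the clinical state. The threshold should be reasonably explained, not clearly explained, so that it meets Doubtful/Unlikely without a new gap.
- Say that the classes are read in order and the first match applies. This settles the existing overlaps, and the corner where Definite is met through a drug level without reasonable timing.
- Align ANNEX 15.

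With these definitions, 12 - 4 = 8 of the 32 well-timed combinations remain Unrelated, none of them with a known pattern.

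**SAP 11.1.** The SAP dates the termination decision to July 2022 and its own version 3.0 to August 2023, so new wording would reach few assessments, if any. For data already collected, add one supplementary table of infusional TEAEs coded Unrelated or with missing causality, by arm, system organ class and preferred term, beside the infusional suspected ADRs. It should not depend on an alternative-cause field, because the AE variables listed in Protocol 9.3.8 contain none. It shows an upper limit for infusional events by arm; later events are outside it.

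**Cost.** A short rewording, one more table, and possibly somewhat higher suspected-ADR percentages.
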